
 
• To assess the effect of Tildrakizumab on IGA mod 2011 (scalp) and PSSI at other measured time points through week 52.
 
• To assess the effect of tildrakizumab on, IGA (scalp only), Scalp Itch NRS, PASI, PGA-S (whole body), IGA mod 2011 (whole body) at week 12 and other measured time points through Week 52.
 
	
 
• Change from baseline in IGA mod 2011 (scalp) and PSSI at other measured time points through Week 52.
 
• Change from Baseline in IGA (scalp only), Scalp Itch NRS, PASI, PGA-S (whole body), and IGA mod 2011 (whole body) at week 12 and other measured time points through Week 52.
 

Objectives	Endpoints

 
• To assess the time to response.
 
	
 
• Time to 75% reduction in PSSI during the 16-week placebo-controlled treatment period.
 
• Time to IGA mod 2011 (scalp) response during the 16-week placebo-controlled treatment period.
 

 
• To assess the efficacy of tildrakizumab in the improvement of scalp itch as measured by the proportion of subjects achieving a 4-point reduction in Scalp Itch Numeric Rating Scale (NRS) score from Baseline at Week 16 compared with placebo.
 
	
 
• The proportion of subjects achieving a 4-point reduction in Scalp Itch NRS score from Baseline to Week 16.
 

 
• To assess the efficacy of tildrakizumab in the treatment of moderate to severe psoriasis (entire body including scalp) compared with placebo as measured by Psoriasis Area and Severity Index (PASI), IGA mod 2011 (whole body), Physician Global Assessment for skin (PGA-S) score (whole body), and total body surface area (BSA) involvement at Week 16.
 
	
 
• The proportion of subjects achieving PASI 75, PASI 90, and PASI 100 at Week 16.
 
• The proportion of subjects with IGA mod 2011 score (whole body) and PGA-S (whole body) score of “clear” or “almost clear” with at least a 2-point reduction from Baseline to Week 16.
 
• Mean percentage change in total BSA involvement from Baseline to Week 16.
 

Exploratory Objectives	Exploratory Endpoints

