**Statistical methods:**

The primary efficacy endpoint for this study is the proportion of subjects with IGA mod 2011 (scalp) score of “clear” and “almost clear” with at least 2-point reduction from baseline at Week 16. The key secondary efficacy endpoints are the proportion of subjects with at least 90% improvement in the PSSI (PSSI90) from baseline at Week 16, the proportion of subjects with IGA (scalp only) score of “clear” and “almost clear” with at least 2-point reduction from baseline at Week 16, the proportion of subjects with IGA mod 2011 (scalp) score of “clear” and “almost clear” with at least 2-point reduction from baseline at Week 12 and the proportion of subjects with at least 90% improvement in the PSSI (PSSI90) from baseline at Week 12. For each endpoint, the tildrakizumab 100 mg dose will be compared with placebo. Both the primary and key secondary efficacy endpoints will be analyzed with Cochran-Mantel-Haenszel test

[REDACTED]  
using the Intent-to-treat (ITT) population.  
[REDACTED]

[REDACTED]  
[REDACTED]  
[REDACTED] Secondary efficacy and exploratory endpoints that are dichotomous will be analyzed in the same manner as the primary efficacy endpoint using the ITT population. Continuous secondary efficacy and exploratory endpoints will be analyzed using an MMRM procedure [REDACTED]  
[REDACTED]  
[REDACTED]

[REDACTED]

Safety endpoints will be analyzed descriptively based on the Safety Analysis Set (SAS) [REDACTED]. Subjects will be summarized based on the actual treatment they received.

Intent-to-Treat (ITT): All randomized subjects who have received at least one dose of study treatment [REDACTED]. The primary efficacy population will be the ITT. Subjects will be summarized based on their planned treatment assignment [REDACTED].

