
 
To assess the effect of Tildrakizumab on IGA mod 2011 (scalp) and PSSI at other measured time points through week 52.
 
To assess the effect of tildrakizumab on IGA (scalp only), Scalp Itch NRS, PASI, PGA-S (whole body), and IGA mod 2011 (whole body), at week 12 and other measured time points through Week 52.
 
	
 
Change from baseline in IGA mod 2011 (scalp) and PSSI at other measured time points through Week 52.
 
Change from Baseline in IGA (scalp only), Scalp Itch NRS, PASI, PGA-S (whole body) and IGA mod 2011 (whole body), at week 12 and other measured time points through Week 52.
 

 
To assess the time to response.
 
	
 
Time to 75% reduction in PSSI during the 16-week placebo-controlled treatment period.
 
Time to IGA mod 2011 (scalp) response during the 16-week placebo-controlled treatment period.
 

 
To assess the efficacy of tildrakizumab in the improvement of scalp itch as measured by the proportion of subjects achieving a 4-point reduction in Scalp Itch Numeric Rating Scale (NRS) score from Baseline at Week 16 compared with placebo.
 
	
 
Proportion of subjects achieving a 4-point reduction in Scalp Itch NRS score from Baseline to Week 16.
 

 
To assess the efficacy of tildrakizumab in the treatment of moderate to severe psoriasis
 
	
 
The proportion of subjects achieving PASI 75,
 

Objectives	Endpoints

compared with placebo as measured by Psoriasis Area and Severity Index (PASI), IGA mod 2011(whole body), Physician’s Global Assessment for Skin (PGA-S) (whole body), and total body surface area (BSA) involvement at Week 16
	
PASI 90, and PASI 100 at Week 16.
 
 
• The proportion of subjects with IGA mod 2011 (whole body) and PGA-S (whole body) of “clear” or “almost clear” with at least a 2-point reduction from Baseline to Week 16.
 
• Mean percentage change in total BSA involvement from Baseline to Week 16.
 

Exploratory Objectives	Exploratory Endpoints

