
 
• The proportion of subjects achieving PSSI 75 at Week 16.
 
• The proportion of subjects achieving PSSI 100 at Week 16.
 
• Proportion of subjects achieving a 4-point reduction in Scalp Itch NRS score from Baseline to Week 16 compared with placebo.
 
• The proportion of subjects achieving PASI 75, PASI 90, and PASI 100 at Week 16.
 
• The proportion of subjects PGA-S score (whole body) of “clear” or “almost clear” with at least a 2-point reduction from Baseline to Week 16.
 
• Time (days) to IGA mod 2011 (whole body) response during the 16-week placebo-controlled treatment period.
 
• IGA (scalp only), Scalp Itch NRS, PASI, PGA-S (whole body), and IGA mod 2011 (whole body), at week 12 and
 
	
[REDACTED] secondary efficacy endpoints will be analyzed using the same method as for the primary efficacy endpoint [REDACTED]
 
All efficacy endpoints obtained from Week 1 [REDACTED]

Endpoint	Statistical Analysis Methods
other measured time points through Week 52. 
 
IGA mod 2011 (scalp), PSSI measured at other time points through Week 52.
 
	

 
Time (days) to 75% reduction in PSSI during the 16-week placebo-controlled treatment period.
 
Time to IGA mod 2011 (scalp) response during the 16-week placebo-controlled treatment period.
 
	
 Time to PSSI-75 or IGA mod 2011 (scalp), response will be analyzed using the Kaplan-Meier method. 

Exploratory Endpoints	

 
Change from Baseline in DLQI score (total and 6 domain scores) at measured time points through Week 52.
 
	All efficacy endpoints obtained [REDACTED] will be summarized using descriptive statistics.

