ECI	Event of clinical interest
EoS	End of study
EoT	End of treatment
ET	Early termination
FDA	Food & Drug Administration
ICH	International Conference on Harmonization
ICSR	Interim Clinical Study Report
IGA	Investigator Global Assessment
ITT	Intent-To-Treat
LOCF	last-observation-carried forward
M-N	Miettinen-Nurminen methodology
MACE	Major Adverse Cardiovascular Events
MedDRA	Medical Dictionary for Regulatory Activities
MI	Multiple Imputation
mIGA	Modified Investigator's Global Assessment
mITT	Modified Intent-To-Treat
MMRM	Mixed Model Repeated Measures
NCS	Not clinically significant
NRI	Non-responder imputation
NRS	Numeric Rating Scale
OC	Observed Cases
PASI	Psoriasis Area and Severity Index
PGA	Physician's Global Assessment
PGA-S	Physician Global Assessment of Skin
PN	Preferred Name
PP	Per Protocol
PSSI	Psoriasis Scalp Severity Index
PT	Preferred term
SAE	Serious adverse event

SAF	Safety analysis set
SD	Standard deviation
SOC	System organ class
TEAE	Treatment-emergent adverse event
uITT	Uniform Intent-To-Treat

173 **1 INTRODUCTION**

174 This Statistical Analysis Plan (SAP) Amendment has been developed following the review of
175 Sun Pharmaceutical Industries Ltd Protocol TILD-18-20 (Version 01 Amendment 03, dated
176 17 Mar 2020), the corresponding case report form (CRF), SAP Version 2.0 (dated
177 09-June-2021).

178 This SAP describes the analysis sets and specific details for the statistical methods to be used
179 for the analysis and reporting of all efficacy and safety data collected during the conduct of
180 Protocol TILD-18-20 during the initial blinded treatment period to Week 16, double blinded
181 active treatment period from Week 16 through Week 52, and observational safety follow-up
182 from Week 52 to Week 72. This SAP reflects changes to the statistical considerations in the
183 protocol. When needed, this SAP supersedes the statistical considerations identified in
184 Protocol TILD-18-20 and its amendments (as applicable). Where considerations are
185 substantially different, they will be identified as such in this document. [REDACTED]

[REDACTED]

195 This SAP is being written with consideration of the recommendations outlined in the
196 International Conference on Harmonisation of Technical Requirements for Registration of
197 Pharmaceuticals for Human Use (ICH) E9 Guideline entitled “Guidance for Industry:
198 Statistical Principles for Clinical Trials”, the E9 Addendum on Estimands and Sensitivity

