- 238 • To assess the effect of tildrakizumab on IGA (scalp only), Scalp Itch NRS, PASI,
239 PGA-S (whole body), and IGA mod 2011 (whole body), at week 12 and other
240 measured time points through Week 52.
- 241 • To assess the time to response
- 242 • To assess the efficacy of tildrakizumab in the improvement of scalp itch as measured
243 by the proportion of subjects achieving a 4-point reduction in Scalp Itch Numeric
244 Rating Scale (NRS) score from Baseline at Week 16 compared with placebo
- 245 • To assess the efficacy of tildrakizumab in the treatment of moderate to severe
246 psoriasis (entire body including scalp) compared with placebo as measured by
247 Psoriasis Area and Severity Index (PASI), IGA mod 2011 (whole body), Physician
248 Global Assessment for skin (PGA-S) score (whole body), and total body surface area
249 (BSA) involvement at Week 16.

250 **2.3 Exploratory Objective**

251 The exploratory objective of this study is:

- 252 • To assess the effect of tildrakizumab on Quality of Life measured by: Dermatology
253 Life Quality Index (DLQI).

254 **3 OVERALL STUDY DESIGN AND TREATMENT PLAN**

255 The overall study design and treatment plan are described in Sections 4.1 of Clinical Protocol
256 TILD-18-20 [REDACTED]. A brief overview is included below.

257 This is a multicenter, randomized, double-blind, placebo-controlled Phase 3 study to assess
258 the efficacy and safety of tildrakizumab in the treatment of moderate to severe psoriasis of
259 the scalp. The study will enroll approximately 214 subjects with moderate to severe psoriasis

260 of the scalp. Eligible subjects will be randomized to 1 of the 2 arms [REDACTED] Arm A:
261 Tildrakizumab 100 mg, subcutaneous (SC) (n=107) and Arm B: Placebo, SC (n=107).

262 The study will comprise 3 parts:

263 **PART 1: Double-blind Placebo-controlled (Day 1 to Week 16)**

264 After a Screening Period of up to 28 days and on Day 1, all eligible subjects will be
265 randomized 1:1 to receive either tildrakizumab 100 mg or placebo administered by SC
266 injection [REDACTED]. Subjects should receive the first dose of study
267 treatment within 24 hours of randomization. The treatment period for the double-blind
268 placebo-controlled part of the study is 16 weeks. All assessments of efficacy and safety
269 before or on the date of injection at Week 16 [REDACTED]
[REDACTED] are considered in PART 1.)

271 **PART 2: Double-blind Active Treatment Extension (Week 16 to Week 52)**

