609 treatment period, defined as time in days from Baseline to first achieving a score of
610 “clear” or “almost clear” with at least a 2-point reduction from Baseline through Week
611 16. Subjects who have not achieved IGA mod 2011 (scalp) response by the last visit or
612 Week 16 will be censored at their last available assessment or Week 16 assessment,
613 whichever is later.

614 • Time to achieving PSSI 75 during the 16-week placebo-controlled treatment period,
615 defined as time in days from Baseline to first achieving PSSI 75. Subjects who have
616 not achieved PSSI 75 by the last visit or Week 16 will be censored at their last available
617 assessment or Week 16, whichever is later.

618 • The proportion of subjects [REDACTED] decrease in Scalp itch NRS score from
619 Baseline at Week 16, assessed among subjects with Baseline Scalp Itch NRS [REDACTED]

620 The Scalp itch NRS is a self-administered, single item questionnaire with response
621 options from 0=No Itch to 10=Worst itch imaginable.

622 • The proportion of subjects achieving PASI 75, PASI 90, and PASI 100 [REDACTED]
[REDACTED] at Week 16. Detailed PASI scoring
624 algorithms are provided in Appendix 1 PASI Scoring.

625 [REDACTED]

630 • Mean percentage change in total BSA involvement from Baseline to Week 16.

631 • Change from Baseline at measured time points [REDACTED] Week 52 [REDACTED]
[REDACTED] for the following endpoints:

- 633 ○ IGA mod 2011 (scalp)
- 634 ○ PSSI
- 635 ○ IGA (scalp only)
- 636 ○ Scalp Itch NRS
- 637 ○ PASI
- 638 ○ PGA-S (whole body)
- 639 ○ IGA mod 2011 (whole body)

[REDACTED]

642 4.9.2.2.2 Analyses of Secondary Efficacy Endpoints

643 Binary endpoints

644 The following binary endpoints will be analyzed in a similar manner as the primary efficacy
645 endpoint based on the ITT [REDACTED] population as appropriate using NRI. A CMH test [REDACTED]
[REDACTED] will be used, [REDACTED]

- 648 • PSSI 90 at Week 16 (key secondary endpoint)
- 649 • PSSI 90 at Week 12 (key secondary endpoint)
- 650 • IGA mod 2011 (scalp) response at Week 12 (key secondary endpoint)
- 651 • IGA (scalp only) response at Week 16
- 652 • PSSI 75 at Week 16
- 653 • PSSI 100 at Week 16
- 654 • ≥ 4 -point decrease in Scalp Itch NRS score from Baseline at Week 16
- 655 • PASI 75 at Week 16

- 656 • PASI 90 at Week 16
- 657 • PASI 100 at Week 16
- 658 • PGA-S response at Week 16

659 **Continuous endpoints**

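### Does the Week 16 whole-body IGA mod 2011 responder proportion lack an analysis because Protocol Table 4 and the SAP binary list leave it out?

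*Protocol*

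**What the plan says.** The synopsis lists among the secondary endpoints "The proportion of subjects with IGA mod 2011 score (whole body) and PGA-S (whole body) score of" the two best categories, with a fall of two or more points, at Week 16. Protocol Table 1 (section 3.0) repeats it: "The proportion of subjects with IGA mod 2011 (whole body) and PGA-S (whole body) of" those same categories. Two scales are therefore named, each giving a yes/no outcome. For the method, the synopsis states: "Secondary efficacy and exploratory endpoints that are dichotomous will be analyzed in the same manner as the primary efficacy endpoint using the ITT population".

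Protocol Table 4 lists the analyses. In the row that uses the primary-endpoint method it has a bullet for the PGA-S proportion and none for the IGA mod 2011 (whole body) proportion. The next bullet reads "Time (days) to IGA mod 2011 (whole body) response during the 16-week placebo-controlled treatment period". The row for time-to-event endpoints says "Time to PSSI-75 or IGA mod 2011 (scalp), response will be analyzed using the Kaplan-Meier method" and does not mention a whole-body time.

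SAP 2.2 keeps the whole-body scale in the Week 16 comparison with placebo: "Psoriasis Area and Severity Index (PASI), IGA mod 2011 (whole body), Physician" and the remaining measures. The binary list in SAP 4.9.2.2.2, which is analysed by CMH with non-responder imputation, ends with "PGA-S response at Week 16" and has no IGA mod 2011 (whole body) item. The scale does appear in the same section among the variables whose change from baseline is summarised descriptively. The SAP Introduction says that, when needed, "this SAP supersedes the statistical considerations identified in" the protocol.

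**The concern.** Two parallel whole-body scales are pre-specified, and only one has a named comparison. The SAP introduces its binary endpoints as an enumerated list and takes precedence over the protocol. A programmer working strictly from that list would produce a CMH comparison for PGA-S and only descriptive output for IGA mod 2011 (whole body). The visible part of SAP 4.13, which records changes from the protocol, mentions the move of IGA (scalp only) but not this endpoint. If the choice between the scales were left open until after unblinding, a reader could ask about selective reporting.

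The time-to-response bullet adds to the impression of error: it is not a declared endpoint, and it stands in a row whose visible method is for proportions.

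**Working it through.** No figure in the plan is at issue, so the check is an item-by-item comparison of the lists.

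**Dichotomous secondary endpoints in Protocol Table 1**
- Key: PSSI 90 at Week 16, IGA (scalp only) at Week 16, IGA mod 2011 (scalp) at Week 12, PSSI 90 at Week 12. That is 4.
- Other, all at Week 16: PSSI 75, PSSI 100, scalp itch, PASI 75, PASI 90, PASI 100, IGA mod 2011 (whole body), PGA-S. That is 8.
- Total: 4 + 8 = 12.

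**Coverage**

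| Source | Named | Missing |
|---|---|---|
| Protocol Table 4 | 4 key + 7 other = 11 of 12 | IGA mod 2011 (whole body) |
| SAP 4.9.2.2.2 binary list | 3 key + IGA (scalp only) + 7 other = 11 of 12 | IGA mod 2011 (whole body) |

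The SAP list occupies printed lines 648 to 658. That is 658 − 648 + 1 = 11 lines with 11 visible items, so redaction hides no item of that list.

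**Whole-body objective at Week 16.** The endpoints are PASI 75, PASI 90, PASI 100, IGA mod 2011, PGA-S and percentage change in BSA, 6 in all. Five have a named between-arm analysis: four by CMH and BSA by the mixed model.

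**Time-to-response endpoints.** Table 1 has 2 (PSSI 75 and IGA mod 2011 scalp), the visible SAP defines and analyses the same 2, and Table 4 has 3.

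**What an analyst needs to fill the gap, and where it stands**
- Definition of response: synopsis and Table 1.
- Test: the synopsis rule for dichotomous secondary endpoints, which points to the primary method (CMH).
- Analysis set: ITT, by that rule and by SAP 4.9.2, which uses ITT for all efficacy endpoints other than the primary one.
- Missing data: non-responder imputation, as for every other binary endpoint in SAP 4.9.2.2.2.
- Data: Protocol 8.0 has the scale assessed at each visit, and inclusion criterion 4 requires a score of at least 3 at Screening and Baseline.

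Nothing has to be invented. No passage gives this proportion a different method, and no visible passage removes it. The SAP Introduction also says that substantial departures from the protocol will be identified, so silence in a list is a weak basis for reading a removal.

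**Consequence if the comparison were not run.** Protocol 9.4 reserves inference for the primary and key secondary endpoints and calls all other comparisons descriptive. SAP 4.9.2 and 4.9.2.3 plan summaries of the efficacy endpoints by arm and by visit in any case. What would be lost is one descriptive p-value and risk difference for a non-key endpoint.

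**The case for a change.** The strongest case for acting is that the SAP list is closed, unredacted and senior to the protocol, so the synopsis rule may never reach the programmer. That stands as a description of the list: the item is absent, and redaction does not explain it. One more bullet would cost almost nothing.

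It does not carry further. The SAP takes precedence only where needed, and on this endpoint it states nothing that competes with the protocol. The selective-reporting worry is limited because the endpoint is on record in both protocol endpoint lists, so leaving it out of the report would be visible.

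It could also be argued that Table 4 does name the scale, in the bullet on whole-body and other scores at Week 12 and further time points through Week 52. That is not a secure answer. Table 1 describes the matching item as change from baseline, and PGA-S appears in that bullet as well as having its own responder bullet.

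Redaction weakens the charge of omission in the rest of the SAP. Lines 625 to 629 are blacked out between the PASI and BSA endpoints, where Table 1 places the joint IGA/PGA-S item. PGA-S response, which the SAP does analyse, has no visible entry in that endpoint list either. Text after the list of descriptive variables and much of 4.13 are also hidden.

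On the time-to-response bullet, the method cell of that Table 4 row is partly blacked out, so it cannot be shown that a test for proportions was meant for a time variable.

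**Conclusion.** The concern identifies a real omission but no defect that calls for a change. It is a gap that the plan's own rule fills, together with a clerical stray bullet in a summary table. Its size is 1 of 12 dichotomous secondary endpoints and 1 of 6 whole-body endpoints at Week 16, with none of the primary or key secondary comparisons affected. Type I error, sample size, the primary result and the scalp conclusions stay as they are, and PASI, PGA-S and BSA still address the whole-body objective between arms.

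The conclusion assumes that analysts read the SAP list together with the synopsis rule, and that comparisons outside the primary and key secondary set stay descriptive, as Protocol 9.4 says. It does not depend on what the blacked-out SAP lines contain. If they define the endpoint, the case for applying the rule is stronger. If they record its removal, the question is closed.

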**9.4.2 Safety Analyses**

All safety analyses will be performed on the Safety Analysis Set based on the actual treatment they received. All the safety will be summarized by-treatment arm and by-subject listings will be provided.

**9.4.2.1 Adverse events and Serious Adverse Events**

Treatment-emergent adverse events are defined as AEs that first occurred or worsened in severity after the first administration of study treatment.

Adverse events will be coded using the Medical Dictionary for Regulatory Activities. For each study treatment, numbers of TEAEs and incidence rates will be tabulated by preferred term and system organ class.

Treatment-emergent AEs by maximum severity, TEAEs by relationship to study treatment, SAEs, TEAEs leading to death, and TEAEs leading to discontinuation of study treatment will be

tabulated for each treatment arm. Commonly occurring TEAEs, [REDACTED] in either treatment arm, will be summarized using descriptive statistics.

The safety of tildrakizumab will be evaluated by and reported as the percentage of subjects for the following TEAEs:

- Incidence, seriousness and severity of all AEs, death cases and discontinuations from the study.
- Percentage of subjects with severe infections, defined as any infection meeting the regulatory definition of a serious adverse event, or any infection requiring IV antibiotics whether or not reported as a serious event as per the regulatory definition.
- Percentage of subjects with malignancies (excluding carcinoma in situ of the cervix).
- Percentage of subjects with non-melanoma skin cancer.
- Percentage of subjects with melanoma skin cancer.
- Percentage of subjects with MACE [REDACTED]
- Percentage of subjects with study treatment-related hypersensitivity reactions (eg, anaphylaxis, urticaria, angioedema, etc).
- Percentage of subjects with injection site reactions (eg, pain, erythema, edema, etc).

